7.2.4 Specimen Shipment

Transport under cold chain conditions. See details in central laboratory manual.

7.3 Study Schedule

7.3.1 Screening

D - 14 to D - 2

- Sign the ICF.
- PD-L1 immunohistochemistry results.
- Collect demographic data.

- 4) Inquire and record medical history (including personal history, past history, allergy history, and cancer history).
- 5) Tumor stage.
- 6) Pathological test results within 1 year before screening.
- 7) Vital signs.
- 8) Physical examination.
- 9) 12-lead ECG.
- 10) Cardiac function score: scored according to NYHA standards
- 11) ECOG score.
- 12) Chest x-ray (not required if chest CT results are available).
- 13) Enhanced CT/enhanced MRI/PET-CT (results of examinations conducted at the study site or other tertiary hospitals within 30 days prior to enrollment are acceptable).
- 14) Laboratory tests: blood routine, blood biochemistry, electrolyte, coagulation function, urine routine, serum virology, thyroid function tests, and serum pregnancy test (only for female subjects of childbearing age). Serum virology can accept results within 28 days before screening, while other laboratory tests can accept results within 7 days before screening.
- 15) Review compliance with inclusion/exclusion criteria.
- 16) Record concomitant medications.

7.3.2 Baseline Period

D-1

- 1) Review compliance with inclusion/exclusion criteria for the second time
- 2) Enrollment (Subjects can be enrolled in the relevant department due to primary tumor before D-1 and after D1 and complete the trial period during hospitalization) .
- 3) Record concomitant medications.

7.3.3 Study Period

D1

- 1) Following successful enrollment at screening, intravenous catheter (for blood sampling) will be placed in regular locations (eg, superficial veins of the upper extremities, superficial veins of the lower extremities, etc.)
- 2) ADA: Collect blood samples within 30 min prior to administration for the detection of anti-SNA002 antibody in the central laboratory.
- 3) Administration drug: another indwelling needle (used for administration) was placed on the contralateral side of the blood collection vein, $[^{68}\text{Ga}]$ Ga-NOTA-SNA002 was slowly injected intravenously, the injection time was not less than 1 min, and extubation was performed after another 10 ~ 20 ml of normal saline was injected, and radiation protection treatment was

performed on the indwelling needle and syringe, and the whole process followed the aseptic operating principles of clinical diagnosis and treatment. Before administration, subject should drink no less than 500 mL of water for hydration.

4) Blood sampling: Blood sampling time points are shown in the table below. ^{68}Ga in the blood samples and centrifugated serum samples are measured using a γ counter within 30 minutes after collection and should be centrifuged within 10 minutes after measuring and the samples are sent to the central laboratory for SNA002 detection.

Blood sampling time (D1)							
Within 30 min before administration	2min ($\pm 1\text{min}$)	5min ($\pm 1\text{min}$)	10min ($\pm 1\text{min}$)	30min ($\pm 2\text{min}$)	50min ($\pm 5\text{min}$)	100min ($\pm 5\text{min}$)	150min ($\pm 10\text{min}$)

5) Systemic PET/CT: Perform whole-body PET-CT scans on subjects after 15 ± 5 minutes, 60 ± 10 minutes, and 120 ± 20 minutes of administration. Panoramic PET-CT scans performed after dosing were acceptable for 1 to 2 subjects in a dose group or each dose group and were required to cover at least one of these time points.

6) Urine sampling: Urine samples are collected at 90 ± 30 min, 180 ± 30 min, and 300 ± 30 min after administration, and ^{68}Ga in urine samples are measured using a γ counter.

7) Measurement of radiation dose: Surrounding radiation dose is measured at 4 ± 0.5 h after administration.

8) Develop a plan for obtaining target lesion specimens (if applicable): Determine whether to collect tissue specimens after administration based on specific circumstances. If the subject has obtained a biopsy specimen within 2 weeks prior to enrollment and has obtained/can undergo immunohistochemical PD-L1 detection results (such as PD-L1 immunohistochemical detection of pathological tissues in different directions of the lesion collected through bronchoscopy within 2 weeks prior to enrollment), and no treatment has been given, no further biopsy is required. Otherwise, pathological specimens need to be collected in this clinical study. The collection method can accept biopsy or surgical resection of specimens, which is determined by the investigators based on the subject's situation.
 (note: the investigators can arrange for the subjects to enter a safe follow-up period after the subjects complete the tissue specimen collection (D2) or surgical specimen collection (D2-D5) during the trial period, or after the subjects who do not need to collect tissue specimens again complete all operations in D1, in order to shorten the waiting time for subsequent treatment from an ethical perspective).

9) Vital signs: Vital signs are evaluated at 6 ± 1 h after administration on D1.

10) Examination of injection site: observe injection site for redness, swelling, heat, pain, itching and other symptoms 6 ± 1 h after administration.

11) Record concomitant medications.

12) Record AEs.

D2 to D5

- 1) Target lesion specimen acquisition: Biopsy specimens can include endoscopic (such as gastroscopy, fiberoptic bronchoscopy, laparoscopy, etc.) and puncture biopsy specimens, which are generally conducted in D2. The preferred specimen for collection is the primary tumor lesion or metastatic lesion with the highest SUVmax; The collection principle is to collect at least one biopsy sample from the target tumor lesions that can be collected, and the maximum number of samples for the same patient is 5. Ideally, biopsies should be performed on both positive and negative lesions of the same patient under PET imaging. The location of specimen collection and the selected collection method will be determined by the investigators based on previous imaging results and the PET results of this experiment. Perform PD-L1 immunohistochemical detection after obtaining target tissue samples.
- 2) If surgical resection is performed, it can be performed on the D2 to D5. Immunotherapy, chemotherapy, or radiation therapy should not be performed on the primary tumor disease during the injection of experimental drugs until the surgery period.
- 3) Vital signs: Vital signs are evaluated at 6 ± 2 h after paracentesis (if performed).
- 4) Physical examination: evaluated at 6 ± 2 h after biopsy (if performed).
- 5) PD-L1 IHC examination: The collected specimens will be sent to the pathology department to make pathological sections as required, and immediately sent by the cold chain transportation company (Shanghai Shengsheng Logistics Co., Ltd.) to an independent third-party central pathology laboratory (Beijing Geenga Medical Laboratory Co., Ltd.) for PD-L1 immunohistochemical examination. The requirements for specimen preparation transported to the central pathology laboratory can be found in the manual of the central pathology laboratory.
- 6) Examination of injection site: observe injection site for redness, swelling, heat, pain, itching and other symptoms 24 ± 6 h after administration on D1.
- 7) Record concomitant medications.
- 8) Record AEs.

7.3.4 Safety Follow-up Period

D6 to D28

- 1) Anti-SNA002 antibody: Blood samples are collected on $D6 \pm 1$ d, $D28 \pm 2$ d and sent to the central laboratory for detection.
- 2) Laboratory examination: blood routine, blood biochemistry, coagulation, and electrolyte tests were conducted on $D6 \pm 1$ d.

- 3) 12-lead ECG: detected on D6 ± 1d.
- 4) Distribute diary cards during the safe follow-up period of D6 ± 1 days (if the subjects discharge immediately after biopsy, the diary cards will be distributed on the day of discharge; if the subjects are not hospitalized, the diary cards will be issued after completing the D1 examination), and collect the diary card on D28 ± 2 days.
- 5) Record AEs: all adverse events should be recorded in the diary cards (if the subjects continue to be hospitalized, adverse events will be recorded in the hospitalization medical record).
- 6) Record concomitant medications: all concomitant medications should be recorded in the diary card (if the subjects continue to be hospitalized, concomitant medications related to primary tumor treatment can be recorded in the hospitalization doctor's order, and medications taken on their own or for long-term underlying diseases can be recorded in the diary cards).
- 7) Trial completion: the study will be completion for subject after the relevant procedures on D28 ± 2d. Subject should be permitted to undergo relevant chemotherapy, radiotherapy and/or immunotherapy for the primary disease during the safe follow-up period.

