Study Design	
Overall Study Design
 
This is an open-label, dose escalation study to evaluate the safety, PK, biodistribution, dosimetry, and tumor targeting potential of SNA002 in patients with solid tumors.
 
This study will consist of Screening Period, Baseline Period, Study Period and Safety Follow-up Period. A signed and dated informed consent form will be obtained before any study-related procedures are performed. Collect CT/MRI/PET/CT results from subjects within one month before screening to obtain baseline tumor assessment. Eligible patients will be enrolled at least two days before the administration of study drug. The radiation dose for all dose groups at the time of administration should be ranged from 37 to 200MBq. Four dose levels of NOTA-SNA002 are planned: 0.1mg, 0.3mg, 0.5mg and 0.9mg. The final drug product administered to the patient is [⁶⁸Ga]Ga-NOTA-SNA002. Three to seven patients will be sequentially enrolled into each dose cohort. Patients will be administered a single dose of SNA002 over 1 minute as an intravenous bolus. Patients will be observed for 6±1h and 24±6h post infusion for infusion-related and other adverse reactions. In the first cohort of patients, whole body imaging will be acquired using PET/CT at 15±5 minutes, 60±10 minutes and 120±20 minutes post-injection. Before each imaging, the patients need to empty bladder as much as possible. Total-body PET-CT scans can be performed on 1-2 subjects in a certain dose group or each dose group, covering at least one of the aforementioned time points. In the subsequent cohorts,

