3. Laboratory examination: Subjects should obtain blood routine (red blood cell count, white blood cell count, hemoglobin, platelet count, neutrophil count, lymphocyte count, monocyte count), blood biochemistry (total protein, albumin, total bilirubin, alanine aminotransferase, aspartate aminotransferase alkaline phosphatase, glucose, creatinine, blood urea nitrogen), electrolyte (potassium, sodium, calcium), thyroid function (thyroid function, triiodothyronine, thyroxine), coagulation function (prothrombin time, thrombin time, fibrinogen), urine routine (bacterial count, glucose, red blood cells, white blood cells), serum virological (hepatitis B virus surface antigen, hepatitis C virus antibody, syphilis specific antibody, human immunodeficiency virus antibody). During the safe follow-up period D6, retest blood routine, blood biochemistry, electrolytes, and coagulation series (note: serum virology can accept results within 28 days before screening, while other laboratory tests can accept results within 7 days before screening).
4. Chest X-Ray: if there is chest CT, it can be ignored.
5. CT/MRI/PET-CT: imaging within one month prior to screening can be acceptable at the research center or other tertiary hospitals.
6. [⁶⁸Ga]Ga-NOTA-SNA002 Administration: slowly inject [⁶⁸Ga] Ga-NOTA-SNA002 intravenously on D1 for at least 1 minute. Before injection, the subjects should drink sufficient water to ensure proper hydration, and the amount of water consumed should not be less than 500mL. After administration, regular drinking and excretion should be carried out to reduce radiation exposure.
7. Blood Sampling: collected within 30 minutes before administration, 2 minutes (± 1 minute), 5 minutes (± 1 minute), 10 minutes (± 1 minute), 30 minutes (± 2 minute), 50 minutes (± 5 minute), 100 minutes (± 5 minute), and 150 minutes (± 10 minute) after administration. Each blood sample should be tested for whole blood radiation dose within 30 minutes after collection, and centrifuged within 10 minutes after measuring whole blood radiation dose. Serum radiation dose should be tested within 5 minutes after centrifugation. After testing, the separated serum samples are divided into cryopreservation tubes, frozen (-60 °C~90 °C), and regularly sent to the central laboratory for SNA002 protein content determination.
8. Urine will be pooled for renal radiotracer clearance before drug administration, 90±30 minutes, 180±30 minutes and 300±30 minutes post injection.

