10.4.4 Safety Analyses

Safety evaluation indicators

- AE/SAE/SUSARs.
- Vital signs: Blood pressure, pulse, respiration, and body temperature.
- Physical Examination: Assessment of changes in physical examination of subjects before and after drug administration.
- Laboratory tests: Blood routine, blood biochemistry, urine routine, and coagulation function.
- Electrocardiogram: Evaluate changes in subjects' electrocardiogram before and after administration.
- Examination of injection site: Evaluate the condition of the injection site after administration, such as redness, swelling, heat, pain, itching, etc.
- Systemic and organ radiation distribution: Regions of interest (ROI) such as the brain, liver, and heart are delineated based on the iteratively reconstructed PET/CT imaging results to obtain the mean and maximum tumor volume radioactivity at different time points. The radioactive decay of each source organ and the radiation dose of all target organs are calculated.
- Radiation exposure in ambient environment: Radiation exposure in ambient environment measured by a radiation detector.
- Researcher exposure: such as recording exposure through personal radiation dosimeters worn by researchers.

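### The only scheduled post-dose laboratory tests and ECG (D6±1) can follow biopsy, surgery or new anticancer therapy, so D6 changes and AEs from D2 in those subjects cannot be assigned to SNA002 by timing

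*Combined protocol and SAP*

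**What the plan says.** **Post-dose laboratory tests and ECG.** Section 7.3.4 states that "blood routine, blood biochemistry, coagulation, and electrolyte tests were conducted on" D6±1, and gives the ECG the same day: "12-lead ECG: detected on D6 ± 1d". The Table 4 footnote on laboratory examination agrees: "During the safe follow-up period D6, retest blood routine, blood biochemistry, electrolytes, and coagulation series". Otherwise these tests appear after dosing only at early termination (7.3.5) or at unscheduled visits (7.3.6).

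**Events that can come between.** Section 7.3.3 puts biopsy generally on D2. For surgery it says "If surgical resection is performed, it can be performed on the D2 to D5". New tissue is expected unless the subject has a specimen from the two weeks before enrolment, has a PD-L1 result or can have one, and has not been treated since. The note to D1 item 8 lets the investigator move a subject into safety follow-up after the specimen is taken, "or after the subjects who do not need to collect tissue specimens again complete all operations in D1". The stated purpose is a shorter wait for treatment. Section 7.3.4 item 7 then says: "Subject should be permitted to undergo relevant chemotherapy, radiotherapy and/or immunotherapy for the primary disease during the safe follow-up period".

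**Early checks.** Vital signs and the injection site are checked at 6±1 h on D1. The Protocol Summary says: "Patients will be observed for 6±1h and 24±6h post infusion for infusion-related and other adverse reactions". The 24±6 h injection-site check is listed in the D2 to D5 block of 7.3.3 and in a Table 4 footnote, with no exemption in any of these places.

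**Analysis.** Section 10.4.4 lists laboratory tests as a safety indicator and plans to evaluate change in the "electrocardiogram before and after administration". It does not mention the timing of biopsy, surgery or new therapy. Section 6.1.1 confirms that there is no control product.

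**The concern.** The before-and-after comparison of laboratory values and ECG rests on one post-dose value. If a resection or a first cycle of chemotherapy falls between the dose and that value, a fall in haemoglobin, a rise in transaminases or a coagulation change has at least two candidate causes. Without a control group, nothing in the design separates them. The same holds for AEs that begin after the procedure or therapy.

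This matters because the decision rules depend on attribution. In 6.1.7.2, escalation stops if at least half of a group have grade 2 or higher adverse reactions, if at least a third have grade 3 or higher ones, or on one serious adverse reaction. In 5.4, the trial ends if over half of the subjects have drug-related AEs of grade 2 or higher, or on one drug-related SAE. The error can run either way: a procedural effect may be charged to SNA002, or a real SNA002 effect may be put down to surgery or chemotherapy.

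**Working it through.** **Plan's own figure.** Four dose levels of 3 to 7 subjects give 4 × 3 = 12 and 4 × 7 = 28, which matches 10.5.

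**Timing, with D1 as the dosing day**

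| Item | Source | Days |
|---|---|---|
| Vital signs and injection site, 6±1 h | 7.3.3 | D1 |
| Observation and injection site, 24±6 h | Protocol Summary, 7.3.3, Table 4 | 18 to 30 h after dosing |
| Biopsy, if performed | 7.3.3 | generally D2 |
| Surgery, if performed | 7.3.3 | D2 to D5 |
| Laboratory tests and ECG | 7.3.4, Table 4 | D6±1 = D5 to D7 |

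- Dose to laboratory tests and ECG: 5 − 1 = 4 to 7 − 1 = 6 days (96 to 144 h).
- D2 biopsy to laboratory tests and ECG: 5 − 2 = 3 to 7 − 2 = 5 days.
- Surgery to laboratory tests and ECG: 5 − 5 = 0 to 7 − 2 = 5 days. On D5 the plan does not say which comes first.
- Therapy started on D2 after release at the end of D1: 3 to 5 days before the laboratory tests and ECG.
- The 24±6 h check: if dosing is between 08:00 and 16:00 (an assumption), the window runs from 02:00 to 14:00 on D2 at one end and from 10:00 to 22:00 on D2 at the other. It therefore falls after a release at the end of D1.

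**Which data are affected**
- D6 laboratory and ECG results are affected in subjects who had a biopsy, surgery or new therapy before the measurement.
- AEs are affected if they start from D2 onward in those subjects.
- AEs before D2, the 6±1 h checks, and subjects with no such event before D5 to D7 are not affected.

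**How easily the grade 3 rule is reached.** In a group of 3, one subject is 1/3 and meets the criterion. In a group of 7, 7/3 = 2.33, so three subjects are needed. Let q be the proportion of subjects with a grade 3 or higher procedure or therapy event that is counted as an adverse reaction. The documents give no value for q, so the values below are assumptions.

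- Group of 3: P = 1 − (1 − q)³. For q = 5%, 10%, 20% this is 1 − 0.857 = 14%, 1 − 0.729 = 27%, 1 − 0.512 = 49%.
- Group of 7: P(at least 3 of 7), exact binomial, gives 0.4%, 2.6% and 15%.

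This illustrates how sensitive a small group is to attribution. It does not predict how often misattribution will occur.

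**Provisions set side by side**
- The early-entry note (7.3.3 D1 item 8, repeated in the Table 4 footnote on enrolment) allows follow-up to begin after D1. The 24±6 h observation and injection-site check are stated for everyone and fall on D2.
- The surgery window (D2 to D5) and the D6±1 window share D5.
- Section 7.3.4 permits immunotherapy in safety follow-up. Section 7.6 prohibits systemic immunotherapy during the trial and requires withdrawal if it is used.

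**The case against.** The strongest reply is that the primary safety endpoint is the incidence of TEAEs and SAEs, which 8.3 records whatever their relation to the drug, with onset time, severity and relationship for each. Concomitant medication is also recorded, and 8.2.2 supplies a causality scale. The protocol names infusion-related reactions as the likely main risk, and the 6±1 h checks precede any D2 procedure. The study is exploratory with no hypothesis test, and early entry to follow-up has a stated ethical reason. All of this stands. It limits the point to D6 laboratory and ECG findings and later-onset AEs, but it does not supply a scheduled post-dose value that is sure to precede the intervening event.

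A reader might go further in four ways that the documents do not support:

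- **That the whole safety endpoint is uninterpretable.** Incidence is counted regardless of cause, and early events are unaffected.
- **That every subject is affected.** Biopsy and surgery happen only if performed, and therapy is permitted, not required. The number affected cannot be derived from the plan.
- **That subjects released after D1 lose the 24±6 h check.** The check is stated without exemption and the early-entry note does not waive it. This is a contradiction, not an omission.
- **That Table 5 forces a post-surgical change into the related category.** One row classes an event as possibly related despite another explanation if de-excitation is positive. The row for events unlikely to be related covers those that lack such proof and have another reasonable explanation. The outcome depends on the assessor's judgement.

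**Conclusion.** The point holds in a limited form. Laboratory tests and ECG have one scheduled post-dose time point, 4 to 6 days after dosing. In subjects who have had a biopsy, surgery or new anticancer therapy by then, changes at that point, and AEs starting from D2, cannot be assigned to SNA002 by timing. The consequence is greatest for the attribution-based escalation and termination rules, where one subject in a group of 3 meets the grade 3 criterion.

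The day counts follow directly from the visit windows. The 14% to 49% range for groups of 3 rests on assumed misattribution rates of 5% to 20%. How many of the 12 to 28 subjects will have an intervening event is unknown.

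A reader might infer that the remedy is an extra blood draw and ECG ahead of any procedure or therapy. That would be a decision on clinical scheduling, and it is not proposed here.

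**What to change.** **Analysis (10.4.4, carried into the SAP that 10.1 promises before database lock)**
- Tabulate TEAEs by onset before or after the first biopsy, surgery or new anticancer therapy.
- Present D6 laboratory shifts and ECG changes separately for subjects with and without such an event before the D6 measurement. Where both fall on D5, state how the order is determined, for example from recorded clock times.

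Onset times and concomitant medication are already collected. The sponsor should confirm that the CRF also captures the dates of procedures and of radiotherapy. The cost is slightly more analysis work, and the subgroups will be small, so the tables remain descriptive.

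**Text to reconcile (this review does not say which rule is right)**
- The early-entry note in 7.3.3 and Table 4 with the 24±6 h observation and injection-site check in the Protocol Summary, 7.3.3 and Table 4.
- The surgery window with the D6±1 window on D5.
- The permission for immunotherapy in 7.3.4 with its prohibition in 7.6.

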7.3.5 Early Termination Visit

- 1) Vital signs.
- 2) 12-lead ECG (If the subject withdraws after D6 and has already undergone examination in D6, it can be unnecessary).
- 3) Laboratory examination: Conduct blood routine, blood biochemistry, coagulation, and electrolyte tests (if the subject withdraws after D6 and has undergone laboratory examination on D6, it may not be conducted again).
- 4) Anti-SNA002 antibody: sent to an independent third-party central laboratory for testing;
- 5) Record AEs.
- 6) Record all concomitant medications.

